13.1 Data Collection and Management Responsibilities

Data collection is the responsibility of the clinical trial staff at the site under the supervision of the site PI. The investigator is responsible for ensuring the accuracy, completeness, legibility, and timeliness of the data reported.

All source documents should be completed in a neat, legible manner to ensure accurate interpretation of data. Black ink is required to ensure clarity of reproduced copies. When making changes or corrections, cross out the original entry with a single line, and initial and date the change. DO NOT ERASE, OVERWRITE, OR USE CORRECTION FLUID OR TAPE ON THE ORIGINAL.

Copies of the electronic CRF (eCRF) will be provided for use as source documents and maintained for recording data for each participant enrolled in the study. Data reported in the eCRF derived from source documents should be consistent with the source documents or the discrepancies should be explained and captured in a progress note and maintained in the participant's official electronic study record.

Clinical data (including AEs, concomitant medications, and expected adverse reactions data) will be entered into Trialmaster, a 21 CFR Part 11-compliant data capture system managed by NYULH DataCore. The data system includes password protection and internal quality checks, such as automatic range checks, to identify data that appear inconsistent, incomplete, or inaccurate. Clinical data will be entered directly from the source documents.

13.2 Study Records Retention

Version: 3.0

Study documents will be retained for the longer of 3 years after close-out, 5 years after final reporting/publication, or 2 years after the last approval of a marketing application is approved for the device for the indication for which it is being investigated or 2 years after the investigation is discontinued and FDA is notified if no application is to be filed or if the application has not been approved for such indication. No records will be destroyed without the written consent of the study staff, if applicable. It is the responsibility of the study staff to inform the investigator when these documents no longer need to be retained.

13.3 Protocol Deviations

A protocol deviation is any noncompliance with the clinical trial protocol, GCP, or Manual of Procedures (MOP) requirements. The noncompliance may be either on the part of the participant, the investigator, or the study site staff. As a result of deviations, corrective actions are to be developed by the site and implemented promptly.

These practices are consistent with ICH E6:

- 4.5 Compliance with Protocol, sections 4.5.1, 4.5.2, and 4.5.3
- 5.1 Quality Assurance and Quality Control, section 5.1.1
- 5.20 Noncompliance, sections 5.20.1, and 5.20.2.

It is the responsibility of the site PI/study staff to use continuous vigilance to identify and report deviations within 1 working days of identification of the protocol deviation, or within 5 working days of the scheduled protocol-required activity.

All protocol deviations must be addressed in study source documents, reported to a specific NIH IC Program Official.

Protocol deviations must be reported to the local IRB per their guidelines. The site PI/study staff is responsible for knowing and adhering to their IRB requirements. Further details about the handling of protocol deviations will be included in the MOP.

13.4 Publication and Data Sharing Policy

This study will comply with the NIH Public Access Policy, which ensures that the public has access to the published results of NIH funded research. It requires scientists to submit final peer-reviewed journal manuscripts that arise from NIH funds to the digital archive PubMed Central upon acceptance for publication.

The International Committee of Medical Journal Editors (ICMJE) member journals have adopted a clinical trials registration policy as a condition for publication. The ICMJE defines a clinical trial as any research project that prospectively assigns human subjects to intervention or concurrent comparison or control groups to study the cause-and-effect relationship between a medical intervention and a health outcome. Medical interventions include drugs, surgical procedures, devices, behavioral treatments, process-of-care changes, and the like. Health outcomes include any biomedical or health-related measures obtained in patients or participants, including pharmacokinetic measures and adverse events. The ICMJE policy, and the Section 801 of the Food and Drug Administration Amendments Act of 2007, requires that all clinical trials be registered in a public trials registry such as ClinicalTrials.gov, which is sponsored by the National Library of Medicine. Other biomedical journals are considering adopting similar policies. For interventional clinical trials performed under NIH IC grants and cooperative agreements, it is the grantee's responsibility to register the trial in an acceptable registry, so the research results may be considered for publication in ICMJE member journals. The ICMJE does not review specific studies to determine whether registration is necessary; instead, the committee recommends that researchers who have questions about the need to

Version: 3.0

register err on the side of registration or consult the editorial office of the journal in which they wish to publish.

FDAAA mandates that a "responsible party" (i.e., the sponsor or designated principal investigator) register and report results of certain "applicable clinical trials":

- Trials of Drugs and Biologics: Controlled, clinical investigations, other than Phase I investigations of a product subject to FDA regulation;
- Trials of Devices: Controlled trials with health outcomes of a product subject to FDA regulation (other than small feasibility studies) and pediatric post market surveillance studies.
- NIH grantees must take specific steps to ensure compliance with NIH implementation of FDAAA.

14 Study Finances

14.1 Funding Source

Charges will be billed only for procedures performed as part of the subject's routine clinical care. All other costs will be charged to the grant funded by the NIH NEI-R01-EY013178.

14.2 Costs to the Participant

Subjects will not be required to pay for any associated costs resulting from this study.

14.3 Participant Reimbursements or Payments

All participating subjects will receive \$20 as compensation for their time.

15 Interest Policy

The PI, [name], has potential conflicts of interest with this project. NYU COI committee have established a management plan that will be implemented for this project.

Version: 3.0

16 References

2. CDC. Don't Let Glaucoma Steal Your Sight! Centers for Disease Control and Prevention. Published November 24, 2020. https://www.cdc.gov/visionhealth/resources/features/glaucoma-awareness.html

3. Orbis International. Global blindness was slowing prior to pandemic study reveals. Orbis. Published October 11, 2021. https://www.orbis.org/en/news/2021/new-global-blindness-data

Version: 3.0

17 Attachments

These documents are relevant to the protocol, but they are not considered part of the protocol. They are stored and modified separately. As such, modifications to these documents do not require protocol amendments.

- 1. New Research Project Feasibility Questionnaire
- 2. Questionnaire for Subjects
- 3. Provisional Patent for the Novel Device
- 4. Recruitment telephone script

Study number: s22-01420 Version: 3.0

18 Schedule of Events

| Study team procedures X Consent subject X Select randomized imaging protocol X Clean first imaging device and attachments X Adjust chin rest / head mount X First imaging session survey X Clean second imaging device and attachments X Adjust chin rest / head mount X Image subject X Second imaging session survey X | Activity | Study Visit |
|--|---|----------------|
| ants | Study team procedures | |
| ants | Consent subject | × |
| stu | Select randomized imaging protocol | × |
| nd attachments | Clean first imaging device and attachments | × |
| nd attachments | Adjust chin rest / head mount | × |
| nd attachments | Image subject | × |
| Clean second imaging device and attachments X Adjust chin rest / head mount X Image subject X Second imaging session survey X | First imaging session survey | × |
| Adjust chin rest / head mount X Image subject X Second imaging session survey X | Clean second imaging device and attachments | × |
| Image subject X Second imaging session survey X | Adjust chin rest / head mount | × |
| Second imaging session survey | Image subject | × |
| | Second imaging session survey | × |

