2.1 Background Information and Relevant Literature

Currently in Ophthalmological Offices, patients that are being imaged on OCT devices often do not have a comfortable patient experience. They tend to move away from the device in order to stretch every so often and oftentimes complain about it. This adds additional time to the imaging process, thereby extending the wait time for the following patients. Furthermore, due to the lack of ability to adjust the chin and forehead rest components to each individual patient's size, the patients tend to move around quite a bit which both lengthens the time, as previously mentioned, as well as increases the likelihood of artifacts, which lead to the misdiagnosis of Glaucoma. This is a catastrophic pitfall as 3 million Americans have Glaucoma, which is the "second leading cause of blindness worldwide. Additionally, there are 43 million people worldwide that suffer from blindness and 77% of those cases could have possibly been prevented by reducing the number of artifacts in their scans. To summarize, the purpose of this invention is to solve the problem in which patients are potentially being misdiagnosed or undiagnosed with ocular diseases as a result of patient discomfort induced movement and subsequent diagnostic testing artifacts which could prevent an efficient intervention to be enacted thereby reducing the patient's chances of suffering from a debilitating eye disease.

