2.3 Rationale

This study primarily focuses on increasing the comfort for each patient's experience as well as reducing motion artifacts by improving the former, as well as stabilizing the patient's head, accomplished by adjusting the chin and forehead rest for each individual patient. The cohort will consist of a total of 90 subjects consisting of subjects that are both healthy and have an existing eye disease, as commonly observed in ophthalmology outpatient offices.

In order for certain limitations to not affect the validity of the results, various aspects of the trial will be randomized. This includes, but is not limited to, the order in which a patient will begin being imaged on either device C/N and which eye, OS/OD the Imager will scan first. This can help account for parameters including whether the time it takes to image the patient and/or level of comfort is affected as a result of their degree of alertness, energy level, how they are feeling on that particular day, etc.

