5.6 Total Number of Participants and Sites

Recruitment will end when approximately 150 participants are enrolled at NYUMC.

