7.2 Imaging Procedures

- Chin and forehead rest will be adjusted for each individual subject by following the appropriate procedure, shown in standard operating procedure attached
- OCT Imaging should include for each eye
 - o Acquisition of 1 image of the Macula
 - Acquisition of 1 image of the ONH
- Two separate questionnaires will be provided to the subject before and after being imaged

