10.2 Sample Size Determination

Let P1 be the proportion of patients who report improvement of comfort and then P0=1-P1 be the proportion of patients who report no difference between two devices. The primary outcome of interest is to see if P_1 is significantly bigger than 50% or not. With sample size of N=90 subjects, we will achieve 80% power to detect that P1 > 65.7% using a two-sided exact test of proportion with a significance level of 0.05. These results assume that the population proportion P1 under the null hypothesis is 50%.

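### Both devices are rated in one visit with no specified interval, no repeated state questions and no order term, so carry-over that differs by device could bias the comfort comparison in either direction

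*Combined protocol and SAP*

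**What the plan says.** Section 4.1 has every subject take part in both arms, and section 5.5 limits participation to a single one-day imaging session. The only description of what separates the two device sessions is in section 18: "First imaging session survey X Clean second imaging device and attachments X Adjust chin rest / head mount X". The list carries no times and neither requires nor forbids a rest.

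The study schematic places the three state questions (well, tired, uncomfortable) before the scans and the comfort questions after them. Section 7.2 agrees: "Two separate questionnaires will be provided to the subject before and after being imaged". Section 18, by contrast, has a survey after each session and no row for the pre-imaging questions. The content of the first-session survey is not described.

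The stated safeguard is random order of device and eye. Section 2.3 says of it: "This can help account for parameters including whether the time it takes to image the patient and/or level of comfort is affected" by alertness, energy or how the subject feels that day. Section 6.1.5 says the envelopes are evenly divided.

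For the analysis, section 10.3 plans an exact test for the preference proportion and a t test for the ratings. It does not say whether the t test is paired, and it names no order, sequence or carry-over term.

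**The concern.** The trial's own premise makes carry-over plausible. Section 2.1 says of patients on current devices: "They tend to move away from the device in order to stretch every so often and oftentimes complain about it". A subject who has just finished on C may sit down at N already stiff, and may rate N lower for it. A subject who started on N may be fresher when C begins.

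Random order deals with fatigue that builds at the same rate whichever device came first. It does not deal with strain that differs by device. Comfort is the primary endpoint, so bias here bears on the main conclusion. The well, tired and uncomfortable answers are not planned before the second device, so the subject's state at that moment could not be reconstructed later.

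**Working it through.** **The plan's own figure.** Section 10.2 states: "With sample size of N=90 subjects, we will achieve 80% power to detect that P1 > 65.7% using a two-sided exact test of proportion". Alpha is 0.05 and the null proportion is 50%. The exact two-sided test at N = 90 rejects in favour of N at 55 or more of 90 (actual two-sided alpha 0.0446). Power at 65.7% is then 84.8%, so the stated 80% is not reproduced and is conservative on its own inputs. At N = 150, the enrolment figure in section 5.6, the cutoff is 88, alpha is 0.0409 and power is 97.0%. The carry-over point does not depend on this discrepancy.

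**Rating scale.** Let τ be the true N-C difference. Let l_C and l_N be the points that residual strain from C or N takes off the second rating.

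- C first: N is rated second, so the observed difference is τ - l_C.
- N first: C is rated second, so the observed difference is τ + l_N.
- Balanced order: the mean is τ - (l_C - l_N)/2.

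A common second-session drop π gives τ - π and τ + π, which average to τ. Equal carry-over cancels in the same way. The bias is half the gap between l_C and l_N.

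With assumed values and τ = 1:

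| l_C | l_N | Mean N-C |
|---|---|---|
| 0.3 | 0.3 | 1.00 |
| 0.3 | 0.1 | 0.90 |
| 0.3 | 0 | 0.85 |
| 0.1 | 0.3 | 1.10 |
| -0.3 (relief after C lifts N) | 0 | 1.15 |

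**Proportional case.** Let D_C and D_N be discomfort on each device, with τ = D_C - D_N. If the same share L persists, then l_C = L·D_C and l_N = L·D_N. The mean is τ - L(D_C - D_N)/2 = τ(1 - L/2). At L = 0.2 the loss is 10%; at L = 0.4 it is 20%. An order factor estimates the gap between the two sequences but leaves their average, and so this bias, unchanged.

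**Preference item.** Suppose the true preference for N is 65.7% and only the C-first half shifts (assumed amounts):

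| Shift in C-first | Pooled P1 | Power, N = 90 | Power, N = 150 |
|---|---|---|---|
| -0.10 | 60.7% | 51.4% | 72.6% |
| -0.05 | 63.2% | 70.1% | 89.1% |
| 0 | 65.7% | 84.8% | 97.0% |
| +0.05 | 68.2% | 93.9% | 99.5% |
| +0.10 | 70.7% | 98.1% | 99.9% |

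A shift of +0.10 in one order and -0.10 in the other leaves pooled P1 at 65.7% and power at 85.3% for N = 90, so a symmetric order effect costs nothing.

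**What an order factor does buy.** A symmetric order effect ±π adds π² to the variance of the within-subject differences under balanced order. A plain t test leaves that in the error; an order factor removes it.

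**Adjusting for current discomfort.** Residual discomfort lowers N-C when C came first and raises it when N came first, so one common coefficient nearly cancels. In a simulation with assumed mean discomfort of 1.5 for C and 1.0 for N (true difference 0.50), the estimate without and with that covariate was 0.451 and 0.448 at L = 0.2, and 0.400 and 0.401 at L = 0.4. The bias stays.

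**The case against.** The strongest reply is that the schedule is silent, not prohibitive. A survey, cleaning and refitting fall between the sessions, and nothing stops a subject from resting. The operating steps for N in section 6.1.5 include settling the subject into a relaxed position and checking comfort before imaging, so in the C-first order some check does precede N. The first-session survey may also ask about state. All of this stands, and it is why the point is that no interval is specified, not that there is none. But nothing makes the gap uniform, the comfort check on N is not said to be recorded, and no equivalent is described for C.

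Second, order is randomised, and section 2.2.2 says there are no clinical data, so neither carry-over nor its direction is shown. That also stands. The preference question asks for a direct comparison, so contrast after C could enlarge the difference.

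Third, carry-over is not beyond reach of analysis. If the first-session survey holds the 0-5 rating, comparing first-session ratings between the two orders is free of carry-over, and comparing sequence totals tests for unequal carry-over, though weakly. Neither is planned. The first would also fail if both ratings are collected together at the end, as the schematic and section 4.2.1 suggest.

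**Conclusion.** The gap is real and worth closing. As written, the plan specifies no interval, no repeat of the state questions and no order term, and randomisation protects only against carry-over that is equal for both devices. The bias in the mean rating difference is (l_C - l_N)/2. It runs toward no difference if C leaves more strain, which the trial's premise suggests, and away from it if relief or contrast after C dominates. The 10% and 20% losses rest on an assumed share L that is the same for both devices, with additive carry-over and balanced order.

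A reader might infer more than the documents support:

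- That strain definitely carries over and shrinks the comfort difference. The direction is conditional and no data exist.
- That L alone fixes the observable preference proportion. It does not, because pooling averages two probabilities. On a latent normal scale at L = 0.4, pooled P1 is 62.6%, 61.3% or 58.7% for assumed D_N of 0, 1 or 2.
- That a loss of power can be stated for the ratings. The documents give no standard deviation, expected difference or power for them.
- That ratings and preference are formally co-primary. Section 4.2.1 puts both questions under the primary endpoint, but section 10.2 names only the proportion as the primary outcome of interest, and section 10.3 adds the ratings as a further comparison.

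**What to change.** 1. In section 18 and the schematic, add one interval off both devices between the first-session survey and the second session. Make it the same for every subject, with its length set by the study team.
2. Give the existing three-item questionnaire immediately before each device session, record the answers, and add both occasions to section 18. At the same time, reconcile survey timing across the schematic and sections 4.2.1, 7.2 and 18, and state what the first-session survey contains.
3. In section 10.3, analyse the ratings as within-subject N-C differences with randomised device order as a factor. If the first-session survey holds the 0-5 rating, report the first-session-only comparison as a carry-over sensitivity analysis. It has about 45 subjects per order at N = 90, or 75 at N = 150, so it will be less precise.
4. Do not put the change in the discomfort answer into the primary model as a covariate. It is affected by the first device and does not remove the bias. Summarise it by order instead.

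The interval is what limits carry-over. The repeated questions make it visible, and the order factor removes order-effect variance. The cost is a slightly longer visit and three repeated questions. The analysis change is free, and no extra subjects are needed.
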